### **9.2 Peripheral blood lymphocyte phenotypes**

Lymphocyte subsets (CD3, CD4, CD8, CD19, and CD56) will be analyzed at baseline and after 2 doses according to absolute cell numbers per microliter of whole blood, percent representation among all lymphocytes, and coexpression of the activation markers CD25, HLA-DR, and CD45RO using automated flow cytometric techniques at the Flow Cytometry Core Laboratory, Robert H Lurie Cancer Center of Northwestern University under the supervision of [name].

### **9.3 Specimen Banking**

Patient samples collected for this study will be retained at Robert H Lurie Cancer Center of Northwestern University Pathology Core Facility. Specimens will be stored indefinitely or until they are used up. If future use is denied or withdrawn by the patient, best efforts will be made to stop any additional studies and to destroy the specimens.

[name] will be responsible for reviewing and approving requests for clinical specimen from potential research collaborators outside of Northwestern University. Collaborators will be required to complete an agreement (a Material Transfer Agreement or recharge agreement) that states specimens will only be released for use in disclosed research. Any data obtained from the use of clinical specimen will be the property of Northwestern University for publication and any licensing agreement will be strictly adhered to.

The following information obtained from the subject's medical record may be provided to research collaborators when specimens are made available:

- Diagnosis
- Collection time in relation to study treatment
- Clinical outcome – if available
- Demographic data

## **10.0 STATISTICAL CONSIDERATIONS**

### **10.1 Study Design/Study Endpoints**

A Simon two-stage optimum Phase II design will be used. Up to 33 patients will be entered into the trial. In the first stage, up to 12 patients will be entered to achieve 10 evaluable. If no patients show a response, then the trial will be terminated due to inactivity of the treatment. If 1 or more of 10 show a response, then up to an additional 22 patients will be added to achieve 19 evaluable. If 3 or fewer of 29 show a response, then the trial will conclude that the response rate could be as low as 5%. If 4 or more respond, then the trial will conclude that the response rate is greater than 5%. This design has a 20% chance of falsely concluding the rate is 5% (false negative Type II error rate = 20%, or power = 80%), and a 5% chance of falsely concluding that the rate is 20% (false positive Type I error rate = 5%). There is a 60% probability of early termination of the trial when the true response rate is 5%. Due to inevaluable patients and dropout, target accrual will be up to 33 patients. It is anticipated that 8 patients will be accrued per year so that accrual to this study will take 4 years.

### **10.2 Statistical Analysis**

Response rates and 95% confidence intervals will be calculated using exact binomial probability distributions. Progression-free survival and overall survival will be analyzed using Kaplan-Meier curves. Adverse events will be summarized descriptively using frequencies and percentages. Statistics will be given on type, severity, frequency and attribution of adverse events. Sample size considerations are described above.

An intention to treat analysis will be done. In a single group Phase II study, intention to treat means that all patients who are evaluated and registered for the study are followed and analyzed regardless of (a) whether they were subsequently found to be protocol ineligible and (b) the amount of study treatment (nivolumab) they received. This definition parallels the definition of intention to treat in randomized clinical trials. For response rates, patients will be considered evaluable for response if they meet the criteria in the second paragraph of Section 6.2.1. Otherwise, they are unevaluable for response. The

ITT analysis of response will specify the number of patients unevaluable for response and will determine the response rate in those evaluable for response. For progression-free and overall survival, all registered patients will be included in the analysis, making this ITT. For patients who receive no nivolumab, survival times will be taken from the time of study registration. For toxicity, patients will be considered evaluable for toxicity if they meet the criteria in the first paragraph of Section 6.2.1. Otherwise, they are unevaluable for toxicity. The ITT analysis of toxicity will specify the number of patients unevaluable for toxicity and will perform the toxicity statistical analysis in those evaluable for toxicity.

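### The exact 95% CI for response rate in 10.2 mentions no adjustment for the two-stage stop; read as the usual single-sample interval, it is slightly miscalibrated and at 4/29 includes the 5% that 10.1 says is exceeded (minor)

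*Combined protocol and SAP*

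**What the plan says.** Section 10.1 sets the design and the only decision rule for the primary endpoint:

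- Design: "A Simon two-stage optimum Phase II design will be used".
- Stage 1 size: "In the first stage, up to 12 patients will be entered to achieve 10 evaluable".
- Stage 1 stopping rule: "If no patients show a response, then the trial will be terminated due to inactivity of the treatment".
- Stage 2: if at least one of the 10 responds, "then up to an additional 22 patients will be added to achieve 19 evaluable", for 29 evaluable in all.
- Final rule, negative side: with at most 3 responders in 29, a true rate of 5% is not ruled out.
- Final rule, positive side: "If 4 or more respond, then the trial will conclude that the response rate is greater than 5" (in percent).
- Error rate: "a 5% chance of falsely concluding that the rate is 20% (false positive Type I error rate = 5" (in percent), with 80% power at 20% and a 60% chance of early termination at 5%.

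Section 10.2 gives the whole interval plan for response in one sentence: "Response rates and 95% confidence intervals will be calculated using exact binomial probability distributions". The denominator is the patients evaluable for response. The section does not name the type of exact interval, mention the stage 1 stop, or say how the interval relates to the count rule.

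**The concern.** The primary result will be a response count, a conclusion from the count rule, and a confidence interval. The rule comes from the two-stage distribution and spends about 5% in one tail. The interval, on its usual reading, treats the 29 patients as one fixed sample and spends 2.5% in each tail.

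Two things follow. A single-sample exact interval loses its coverage guarantee once the trial can stop at 0/10. And at the smallest success count, the report would state a response rate above 5% beside an interval that starts below 5%, with nothing in the plan to explain the difference. If that is settled only after the data are seen, the choice of interval at the boundary is open to question.

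**Working it through.** **Inputs.** From 10.1: 10 evaluable in stage 1, stop at 0 responders, 29 evaluable in total, success at 4 or more, reference rates 5% and 20%. From 10.2: 95% level, exact binomial. Assumption: 10.2 means the usual two-sided Clopper-Pearson interval on x/29 (x/10 after a stop).

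**Step 1: reproduce the design.** Let X1 ~ Bin(10, p) and X2 ~ Bin(19, p).
- Early termination at 5%: 0.95^10 = 0.5987 (plan: 60%).
- P(X1 ≥ 1 and X1 + X2 ≥ 4) = 0.0468 at p = 5% and 0.8011 at p = 20% (plan: 5% and 80%).
- A search for the optimal Simon design under these limits returns 0/10 and 3/29.

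The stated design is right. Ignoring the stop, P(X ≥ 4) for a single sample of 29 at 5% is 0.0548. The difference from 0.0468 is the set of paths with none in 10 and then 4 or more in 19: 0.5987 × 0.0132 = 0.0079.

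**Step 2: intervals at the boundary.** The two-stage limits order a stop at 0/10 lowest and then rank by total responders. The lower limit solves P(X1 ≥ 1 and X1 + X2 ≥ x) = a. The upper limit solves 1 − P(X1 ≥ 1 and X1 + X2 ≥ x + 1) = a. Here a is the probability per tail.

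| At 4/29 | 2.5% per tail (95%) | 5% per tail (90%) |
|---|---|---|
| Single-sample | 3.9% to 31.7% | 4.9% to 28.8% |
| Two-stage | 4.1% to 34.3% | 5.1% to 30.8% |

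Only the two-stage 90% interval excludes 5%, so the conflict has two causes, the level and the ignored stop. At 5/29 the single-sample 95% interval is 5.8% to 35.8%, so among success counts only 4/29 is affected. The two-stage 90% lower limit is 3.2% at 3/29, on the other side of 5%.

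**Step 3: how often exactly 4/29 occurs.**

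| True rate | P(exactly 4/29) | P(success) | Share of successes |
|---|---|---|---|
| 5% | 3.4% | 4.7% | 74% |
| 10% | 14.3% | 28.9% | 49% |
| 15% | 17.3% | 58.9% | 29% |
| 20% | 12.0% | 80.1% | 15% |

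**Step 4: coverage of the single-sample 95% interval under the two-stage design.** For true rates of 5% to 20% it runs from 96.8% (at 17.9%) to 99.4%. It falls short near 32%. At p = 32% the interval misses when:
- the trial stops at 0/10, where the upper limit is 30.8%: 0.68^10 = 0.0211;
- it ends with 1 to 4 of 29, where the upper limit is at most 31.7%: 0.0182;
- it ends with 15 or more of 29, where the lower limit is at least 32.5%: 0.0215.

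The sum is 0.0608, so coverage is 1 − 0.0608 = 93.9%. On a grid from 1% to 60%, it is below 95% only between about 31.7% and 32.5%.

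The cause shows at the 4/29 upper limit. At p = 31.66% the single-sample tail P(X ≤ 4) is 0.025. The two-stage tail also counts the paths that stop at 0/10 but would have gone on to 5 or more: 0.0222 × 0.768 = 0.0171. The true tail is therefore 0.042, and the limit is too low (31.7% against 34.3%).

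**Step 5: other evaluable numbers, with 4 responders and the cutoff kept at 4.**

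| Stage 1 / total evaluable | Two-stage P(4 or more) at 5% | Two-stage 90% lower limit |
|---|---|---|
| 10 / 28 | 0.0426 | 5.3% |
| 10 / 29 | 0.0468 | 5.1% |
| 12 / 29 | 0.0500 | 5.0% |
| 10 / 30 | 0.0513 | 4.96% |
| 10 / 31 | 0.0558 | 4.8% |
| 10 / 33 | 0.0654 | 4.6% |

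**The case against.** The case against is strong. Section 10.2 never uses the interval to test 5%. A one-sided 5% count test and a two-sided 95% interval answer different questions and may differ at the boundary, and showing both is common practice. A lower limit of 3.9% at 4/29 is a fair statement of uncertainty. The conflict arises at one count only, and nothing stops a report from explaining it. A two-stage 95% interval also includes 5% at 4/29 (4.1%), so adjusting for the stop does not by itself remove the conflict. A two-stage 90% interval agrees only narrowly and fails at 30 or more evaluable, which accrual of up to 33 allows.

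All of this stands, and it sets the weight of the point. It also means that the 90% interval should be optional. It does not answer the narrower point: the trial's own distribution yields an interval with guaranteed coverage and a properly placed upper limit at almost no cost.

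A reader might infer more than the documents support:
- That the 10.1 rule, or its 5% error rate, is wrong because the interval includes 5%. It is not; the exact error is 0.0468.
- That the planned interval is invalid in general. It is conservative from 5% to 20%, and its shortfall is about one percentage point in a narrow range.
- That 10.2 prescribes an unadjusted interval. It is silent on this; single-sample is the usual reading, not its wording.

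**Conclusion.** The point holds as a minor improvement to how the primary endpoint is estimated. It is not an error in the design, the sample size or the decision rule. On the usual reading of 10.2, the 95% interval falls to about 93.9% coverage near a true rate of 32%, has an upper limit at 4/29 that is 2.6 percentage points too low (34.3 − 31.7), and includes 5% at the smallest success count. That count has a probability of 12% to 17% for true rates of 10% to 20%. The 10.1 count rule is the only decision rule and governs.

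This assumes a single-sample two-sided interval, a stage 1 stop at 0 responders, a final cutoff of 4 and, except in Step 5, exactly 10 and 29 evaluable. If 10.2 was meant as a two-stage interval, the coverage point disappears. The 95% interval would still start at 4.1% at 4/29, and the explanatory sentence would still be needed.

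**What to change.** In 10.2:

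1. Compute the exact 95% CI for response by inverting the two-stage tail probabilities, with a stop at 0/10 ordered lowest and with the realised stage 1 and total evaluable numbers. At 4/29 this gives 4.1% to 34.3%.
2. State that the 10.1 count rule decides and that the intervals are for estimation, so the 95% interval can include 5% at 4/29.
3. Optionally, show the two-stage 90% interval (5% per tail) beside it. With 10 and 29 evaluable, its lower limit exceeds 5% exactly when there are 4 or more responders. Note that this agreement is lost at 30 or more evaluable if the cutoff stays at 4.

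Cost: two or three sentences and a few lines of code. The upper limits are somewhat higher than those of the single-sample interval, and the 90% level, if shown, is less familiar. The design, accrual and decision rule stay as they are.

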#### 3.1 Inclusion Criteria

- 3.1.1 Patients must have a histologically confirmed stage IV or unresectable locally advanced adrenocortical carcinoma,
- 3.1.2 Patients must have disease progressing after treatment with at least one line of therapy including mitotane and/or chemotherapy.

Note: Patients who are deemed ineligible to receive first line treatment with mitotane and/or chemotherapy or who decline first line treatment may be eligible for this study after discussion with the PI.

- 3.1.3 Patients must have measurable disease according to the standard RECIST version 1.1. CT scans or MRIs used to assess the measurable disease must have been completed within 28 days prior to registration.
- 3.1.4 Patients must be of age  $\geq 18$  years at the time of study registration.
- 3.1.5 Patients must exhibit an ECOG performance status of 0-3.
- 3.1.6 Patients must have adequate organ and bone marrow functions:
  - leukocytes  $\geq 2,000/\text{mcl}$

- absolute neutrophil count  $\geq 1,500/\text{mcl}$
- hemoglobin  $\geq 9 \text{ g/dL}$
- platelets  $\geq 75,000/\text{mcl}$
- total bilirubin  $\leq 1.5 \times$  institutional upper limit of normal (ULN)  
(except patients with Gilbert Syndrome, who can have total bilirubin  $< 3.0 \text{ mg/dL}$ )
- AST(SGOT)/ALT(SGPT)  $\leq 3 \times$  ULN  
*NOTE: If liver metastases are present, AST/ALT  $\leq 5 \times$  ULN is permitted*
- Serum creatinine of  $< 3.0 \times$  ULN (upper limit of normal) or creatinine clearance  $> 30 \text{ mL/minute}$  (using Cockcroft/Gault formula below):  
Female CrCl =  $\frac{(140 - \text{age in years}) \times \text{weight in kg} \times 0.85}{72 \times \text{serum creatinine in mg/dL}}$   
Male CrCl =  $\frac{(140 - \text{age in years}) \times \text{weight in kg} \times 1.00}{72 \times \text{serum creatinine in mg/dL}}$

3.1.7 Patients with history of central nervous system (CNS) metastases are eligible if CNS disease has been radiographically and neurologically stable for at least 6 weeks prior to study registrations and do not require corticosteroids (of any dose) for symptomatic management

3.1.8 Females of childbearing potential (FOCBP) must have a negative serum or urine pregnancy test (minimum sensitivity 25 IU/L or equivalent units of HCG) within 24 hours prior to the start of study drug.

NOTE: A FOCBP is *any woman* (regardless of sexual orientation, having undergone a tubal ligation, or remaining celibate by choice) who meets the following criteria:

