### 6.2 Primary Endpoint

The primary endpoint of this study is overall response rate to treatment and all patients who received at least one dose of nivolumab will be considered for evaluation of response to therapy. For the purposes of this study, patients should be re-evaluated for response every 8 weeks. Overall response will be calculated by sum of the complete and partial response rates according to measurement of target and non-target lesions as described below.

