#### 6.2.1 Definitions:

Evaluable for toxicity. All patients will be evaluable for toxicity from the time of their first treatment with nivolumab.

Evaluable for objective response. Only those patients who have measurable disease present at baseline, have received at least one dose of therapy, and have had their disease re-evaluated will be considered evaluable for response. These patients will have their response classified according to the definitions stated below.

Evaluable non-target disease response. Patients who have lesions present at baseline that are evaluable but do not meet the definitions of measurable disease, have received at least one dose of therapy, and have had their disease re-evaluated will be considered evaluable for non-target disease. The response assessment is based on the presence, absence, or unequivocal progression of the lesions.

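### Section 10.2 calls an evaluable-only response rate ITT, against its own definition of ITT, and plans no response rate in all treated or all registered patients

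*Combined protocol and SAP*

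**What the plan says.** Section 10.2 announces an intention-to-treat analysis and defines it: "intention to treat means that all patients who are evaluated and registered for the study are followed and analyzed regardless of" later-found ineligibility and the amount of nivolumab received. For the time-to-event endpoints it follows that definition: "For progression-free and overall survival, all registered patients will be included in the analysis, making this ITT".

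For response it refers to the second paragraph of Section 6.2.1 and states that the "ITT analysis of response will specify the number of patients unevaluable for response and will determine the response rate in those evaluable for response". Under that paragraph, only patients who have measurable disease at baseline, "have received at least one dose of therapy, and have had their disease re-evaluated will be considered evaluable for response".

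Three other places bear on the denominator:

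- Section 3.1.3 makes measurable disease an entry condition: "Patients must have measurable disease according to the standard RECIST version 1.1".
- Section 6.2 says that "all patients who received at least one dose of nivolumab will be considered for evaluation of response to therapy". It does not say that these patients form the denominator, or how a patient with no assessment is classified.
- Section 10.1 sets the Simon looks in evaluable patients. For stage 1: "In the first stage, up to 12 patients will be entered to achieve 10 evaluable". The final rule is applied to 29 evaluable patients, with allowance for losses: "Due to inevaluable patients and dropout, target accrual will be up to 33 patients".

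**The concern.** Within one paragraph, ITT means all registered patients for PFS and OS but only evaluable patients for response. The response version departs from both limbs of the definition. A registered patient later found to have no measurable disease is dropped despite the clause on ineligibility. A patient who received no nivolumab is dropped despite the clause on amount of treatment. Stating how many were unevaluable does not put them in the denominator.

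Among eligible treated patients, measurable disease and at least one dose are already met. The condition that can still remove someone is never having been re-evaluated. The first scheduled scan is at about week 8 (Sections 5.0 and 6.1), so these are patients who die, withdraw consent or are lost early. They have no documented response, so leaving them out can only raise the rate. A reader who sees an ITT response rate will assume that early failures are counted in it.

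**Working it through.** **1. Reproduce the design (Section 10.1).** Inputs: stage 1 has 10 evaluable patients and stops at 0 responders; the total is 29 evaluable; activity is concluded at 4 or more responders; the null rate is 5% and the alternative 20%.

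- Early termination at rate p: (1-p)^10. At 5%: 0.95^10 = 0.5987.
- Probability of concluding activity: sum over x = 1 to 10 of P[Bin(10,p) = x] × P[Bin(19,p) ≥ 4-x]. At 5%: 0.0468. At 20%: 0.8011.

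The plan states 60%, 5% and 80%. All three agree, for evaluable patients.

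**2. Look for a rule that restores the dropped patients.**

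| Section | What it settles |
|---|---|
| 6.2 | Dosed patients are considered for response; no denominator, no non-responder rule |
| 6.2.1 | Re-evaluation required |
| 10.2 | Response rate in evaluable patients only; number unevaluable reported |
| 4.5 | Imaging continues after stopping for toxicity, so stopping does not by itself make a patient unevaluable |
| 5.0, note 3 | Tumor assessment includes clinical criteria, so some deteriorating patients may count as re-evaluated |
| 4.7 | Replacement covers untreated patients only |

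None counts a treated, never re-evaluated patient as a non-responder, and none plans an all-treated or all-registered response rate.

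**3. Size of the shift.** Let N patients be treated, with a share d never re-evaluated and none of those a responder. With r responders, the evaluable rate is r/[N(1-d)] and the all-treated rate is r/N. Their ratio is 1/(1-d).

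The documents give no value for d. They give only the cap of 33 for 29 evaluable, so I assume that 1 to 4 of the extra places are treated non-responders. Intervals are exact binomial (Clopper-Pearson), in line with Section 10.2.

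| Denominator | Factor vs 29 | 4 responders (exact 95% CI) |
|---|---|---|
| 29 | 1.00 | 13.8% (3.9–31.7) |
| 30 | 30/29 = 1.03 | 13.3% (3.8–30.7) |
| 31 | 31/29 = 1.07 | 12.9% (3.6–29.8) |
| 32 | 32/29 = 1.10 | 12.5% (3.5–29.0) |
| 33 | 33/29 = 1.14 | 12.1% (3.4–28.2) |

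With 6 responders, 6/29 = 20.7% (8.0–39.7) and 6/33 = 18.2% (7.0–35.5). The two point estimates lie on either side of the 20% design rate.

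**4. Type I error, under one reading only.** Suppose the 5% null referred to all treated patients and d = 4/33 = 12.1%, all early failures. The rate among evaluable patients under the null is then 0.05/(1-4/33) = 0.0569. Putting 0.0569 into the formula in step 1 gives 6.9%, if 10 and 29 evaluable are always reached. Applying the entry caps (stage 1 ends at 10 evaluable or 12 entered; stage 2 at 29 evaluable or 33 entered) gives 6.2% to 6.4%. That range covers a stage 2 limit of 21 added patients (Study Summary), 22 (Section 10.1), or the total cap alone. If the 5% null refers to evaluable patients, the same caps and d give 4.2% to 4.3%.

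**The case against.** The strongest reply is that nothing the trial decides depends on this. The go/no-go rule counts responders among evaluable patients, and Sections 6.2.1, 10.1 and 10.2 use that population consistently for response. Section 10.2 says exactly what its response analysis contains, uses the same form for toxicity, and requires the number unevaluable to be reported. On that view the target is the rate in evaluable patients, so there is no bias relative to it, and a reader can work out the lower rate.

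The number affected may also be small. Clinical criteria can count as re-evaluation, and Section 5.0 schedules a tumor assessment at end of treatment. Some of the four extra places may go to patients who were never treated, and consent withdrawals are not necessarily treatment failures. No rule compares the observed rate with 20%, so the six-responder example has no formal consequence.

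Most of this stands as a limit on size. The decision rule is unaffected, d is unknown, and the figures for 33 are the upper case within the entry cap. It does not remove the contradiction. The paragraph supplies its own meaning of ITT, and the response analysis does not meet it. Repeating the form for toxicity repeats the label problem. A bare count of unevaluable patients does not show how many were treated, so it may not be enough to recover the all-treated rate.

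**Conclusion.** The point holds and should be fixed. The fault is in the label and the denominator of the reported primary estimate, not in the Simon design. Relative to an all-treated rate, the reported rate is too high by a factor 1/(1-d). With 29 evaluable and one to four treated, never re-evaluated patients, that is 1.03 to 1.14, or at most 1.7 percentage points at four responders (13.8% less 12.1%). This is small beside the confidence interval, but its direction is fixed. The size rests on the assumed number of such patients. The rise in type I error to 6.2–6.4% applies only if the 5% null was meant for all treated patients, which the documents do not say.

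**What to change.** In Section 10.2:

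1. Stop calling the evaluable-only response rate ITT; call it the rate in response-evaluable patients.
2. Report beside it, with an exact 95% interval, the rate in all patients who received at least one dose, counting every never re-evaluated patient as a non-responder.
3. If the ITT label is kept for response, also report the rate in all registered patients. That is the population Section 10.2 defines as ITT and uses for PFS and OS; an all-treated rate alone would not meet the definition.
4. State the number unevaluable by reason, separating treated from untreated patients.

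Keep the looks at 10 and 29 evaluable patients with cut-offs 0 and 3. Those cut-offs should not be carried over to 12 and 33 patients, where the type I error would be 7.1%.

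The cost is wording in one section and one or two extra reported rates. It needs no extra patients and does not change the looks, cut-offs or power.

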### **2.2 Secondary Objectives & Endpoints**

- 2.2.1 To assess the progression free survival defined as time from date of first nivolumab infusion until date of death or evidence of progression of disease as assessed by CT imaging every 8 weeks according to RECIST criteria 1.1.
- 2.2.2 To assess the overall survival defined as time from date of first nivolumab infusion until death of patients with metastatic or locally advanced ACC. The patients will be assessed for survival (either by routine clinic visit or by phone) every 2 weeks while on treatment and every 3 months for up to 2 years after completion of trial to document survival and disease progression,
- 2.2.3 To assess the safety and tolerability profile of nivolumab described by number, frequency, and severity of adverse events according to the National Cancer Institute Common Terminology Criteria for Adverse Events (CTCAE) version 4.0.3 assessed every 2 weeks while patients are on therapy.

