#### **4.5 Duration of Follow Up**

All patients will be followed for adverse events for 12 weeks after last dose of nivolumab, or until the patient starts a new treatment, whichever occurs first. Patients who discontinue treatment for unacceptable adverse event(s) will be followed until resolution or stabilization of the adverse event (i.e. the grade is not changing). If a patient stops treatment due to unacceptable adverse event(s) but has not demonstrated disease progression, then the patient will be followed with imaging studies every 8 weeks until the time of progression radiographically according to RECIST 1.1 criteria. In the event that a radiographic response is detected, then this event will be included as a response in the final analysis, and the time of progression used in calculation of the survival analysis. Patients will be followed for survival status every 3 months for 2 years after treatment discontinuation or until death, whichever occurs first.

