**4.7 Patient Replacement**

Any patient who signs consent but does not receive study treatment may be replaced.

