### **6.3 Secondary Endpoints**

PFS is defined as the duration of time from start of treatment to time of progression or death, whichever occurs first. Progression assessment will be performed by investigator each time the patients has a radiologic evaluation after 8 weeks of treatment. OS is defined as the duration of time from start of treatment to time of death.

Safety and tolerability will be measured by the incidence of all adverse events, serious adverse events, deaths and laboratory abnormalities. Adverse event assessments and laboratory tests will be performed at baseline, and continuously throughout the study at the beginning of each subsequent cycle.

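### Section 10.2 puts two time origins on one PFS curve and one OS curve: registration for never-treated patients, first infusion for everyone else

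*Combined protocol and SAP*

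**What the plan says.** **Endpoint definitions.** Section 2.2.1 defines PFS as "time from date of first nivolumab infusion until date of death or evidence of progression of disease", and 2.2.2 has "overall survival defined as time from date of first nivolumab infusion until death". Section 6.3 words the same origin as start of treatment: "PFS is defined as the duration of time from start of treatment to time of progression or death, whichever occurs first", and "OS is defined as the duration of time from start of treatment to time of death".

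**Analysis set.** Section 10.2 states: "For progression-free and overall survival, all registered patients will be included in the analysis, making this ITT". It then gives a separate origin for one subgroup: "For patients who receive no nivolumab, survival times will be taken from the time of study registration". It does not change the origin for treated patients, so the definitions in 2.2 and 6.3 continue to apply to them. The same section compares its intention-to-treat definition with that of randomized trials, and says that registered patients are followed whatever amount of nivolumab they received.

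**Follow-up.** Section 4.5: "Patients will be followed for survival status every 3 months for 2 years after treatment discontinuation or until death, whichever occurs first". Footnote 11 of the procedures table in 5.0 sets contact every 2 weeks on treatment and every 3 months for up to 2 years off treatment. Section 2.2.2 counts the 3-monthly contact from completion of the trial.

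**Untreated patients.** Section 4.7: "Any patient who signs consent but does not receive study treatment may be replaced". Sections 3.0 and 11.3 require registration before treatment. No section limits the interval from registration to first dose.

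**The concern.** A Kaplan-Meier curve answers a question of the form: what proportion of this population is still event-free at time t after this starting event? Here the starting event differs between patients, and which one applies is settled after registration by whether the patient reaches a first dose. The time between registration and dose is dropped for those who reach it and kept for those who do not, including any early deaths.

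The randomized-trial parallel in 10.2 does not cover this. There, everyone shares one time zero whatever treatment follows.

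PFS and OS are the named secondary efficacy endpoints and come from at most 33 patients, so a few early events can move a median. Readers who set these medians beside other advanced-disease results need to know the starting event and the population.

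**Working it through.** **Side by side**

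| | Treated | Registered, never treated |
|---|---|---|
| On the PFS and OS curves? | Yes (10.2) | Yes (10.2) |
| Time zero | First infusion (2.2.1, 2.2.2, 6.3) | Registration (10.2) |
| Survival contact | On treatment, then 3-monthly (4.5, footnote 11) | Promised in general terms (10.2); no start point |
| Scans | By cycle from Cycle 3 Day 1 (5.0) or by week (6.1) | No schedule stated |

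The plan gives no median, event count or power for PFS or OS, so there is no figure of its own to reproduce. The Simon figures do not depend on these endpoints. They do reproduce: early termination at a 5% response rate is 0.95^10 = 0.599 (stated 60%), power is 0.801 (stated 80%) and type I error is 0.047 (limit 5%).

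**Illustration.** Inputs from the documents:
- treated medians m of 2 and 5 months, the PFS figures in 1.1 for the first-line trial;
- 11.8 months, an OS figure in 1.1 from the placebo-controlled trial;
- 33 patients at most, 29 evaluable, so an allowance of 33 − 29 = 4 (10.1).

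Assumptions, none stated in the documents:
- exponential times, with no other censoring;
- k = 4 untreated;
- untreated patients have twice the hazard;
- a fixed gap g of 1, 2 or 4 weeks, which is 0.23, 0.46 or 0.92 months at 4.345 weeks per month.

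Put x = 2^(−t/m). The mixed curve has its median where (29/33)x + (4/33)x² = 0.5, that is 4x² + 29x − 16.5 = 0. So x = (−29 + √(841 + 264))/8 = 0.530, and the median is −m·log2(0.530) = 0.915m.

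With registration for everyone, treated times lengthen by g and the equation becomes 4x² + 29·2^(g/m)·x − 16.5 = 0. For m = 2 and g = 0.46, 29 × 2^0.23 = 34.02, so x = (−34.02 + √(1157.2 + 264))/8 = 0.460 and the median is 2.24.

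| Treated median (months) | Mixed origin (10.2) | Registration for all: gap 1, 2, 4 weeks | Treated only, first infusion |
|---|---|---|---|
| PFS 2 | 1.83 | 2.03, 2.24, 2.66 | 2.00 |
| PFS 5 | 4.58 | 4.78, 4.98, 5.39 | 5.00 |
| OS 11.8 | 10.8 | 11.0, 11.2, 11.6 | 11.8 |

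Under these assumptions the mixed median lies 0.2 to 0.8 months below the registration median and 0.2 to 1.0 months below the treated-only median.

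**Sensitivity**
- *Number untreated.* With k untreated the mixed equation is kx² + (33 − k)x − 16.5 = 0. It gives 1.00m, 0.98m, 0.96m and 0.915m for k = 0, 1, 2 and 4. With k = 0 the mixed curve is the first-infusion curve.
- *Prognosis of the untreated.* At equal hazard the mixed median equals m. At half the hazard with k = 4, put y = √x. Then 29y² + 4y − 16.5 = 0, y = 0.688, x = 0.474 and the median is 1.077m, or 2.15 for m = 2. The direction is therefore not fixed by the design.
- *No follow-up at all.* Patients censored at day 0 leave the risk set before any event, so the curve is identical to the treated-only curve.

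**The case against.** The rule is stated in advance and reproducible, and Amendment 2 added the intention-to-treat plan on purpose. PFS and OS are secondary and described by Kaplan-Meier curves, with no test or target. Few patients are likely to be affected: registration follows confirmation of eligibility, the allowance of 4 also covers treated patients who are never re-evaluated, and 4.7 speaks of consent rather than registration. All of this stands and limits the weight of the point. It does not remove the two origins, because 10.2 itself writes the rule for untreated patients.

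Four stronger readings are tempting, and the documents do not support them.

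- *Never-treated patients get no follow-up and would be censored at about day 0.* Section 10.2 says registered patients are followed whatever they received. The off-treatment wording of footnote 11 can be read to include them, and 4.6 separates stopping treatment from withdrawing consent. What is missing is a start point, contact times and a scan schedule. Censoring at day 0 would be conjecture, and it would also remove the mixing.
- *The curves have no single meaning.* This is too strong: with no untreated patients each curve has exactly the meaning given in 2.2.
- *The distortion is 5% to 23%.* A reader might divide an assumed gap of 1 to 2 weeks by a median: 7/(2 × 30.44) = 11% to 14/(2 × 30.44) = 23% for 2 months, and 5% to 9% for 5 months. That measures the choice of first infusion over registration for treated patients. It would be the same with nobody untreated, so it does not measure mixing.
- *The rule flatters the drug.* No such direction is shown. If untreated patients fare worse, the mixed median is the lowest of the three in the table above.

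**Conclusion.** The point holds in a limited form. Once any registered patient goes undosed, the 10.2 curves match neither the registered-population nor the treated-population quantity.

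The size cannot be fixed from the documents, because they state neither the number untreated nor the registration-to-dose interval. It is nil with no untreated patients. With 1 to 4 untreated at an assumed doubled hazard, the mixed median falls about 2% to 8% below the treated-only median. The illustrative medians are borrowed: 2 and 5 months come from first-line treatment, whereas this trial enrols mainly pretreated patients.

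The stopping rule, the sample size and the response conclusion do not change. This is a worthwhile correction to the secondary analyses and does not threaten the trial's main result.

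**What to change.** Use one origin per curve.

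1. In 10.2, measure PFS and OS from registration for every patient in the all-registered analysis. Report the first-infusion definition of 2.2.1 and 2.2.2 in treated patients only.
2. State which of the two is the secondary endpoint, and align 2.2 and 6.3 with that choice.
3. Report the number of registered patients never treated.
4. In 4.5 and footnote 11, anchor the existing 3-monthly contact, for both survival and progression status, at registration for never-treated patients. This gives a start point to the follow-up that 10.2 already promises.
5. In 10.2, state how PFS is censored for a never-treated patient with no scan. Survival contact alone would leave the PFS curve undefined for these patients.

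The cost is a few sentences across 2.2, 4.5, 5.0, 6.3 and 10.2, two versions of each curve to report, and a few telephone contacts. No information is lost, and the existing first-infusion result is kept.
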